**Figure 1: Study Design**

### 3.1. Control of Type I Error

All statistical analyses are exploratory in nature. Unless otherwise specified, all confidence intervals (CIs) provided will be at the 95% confidence level.

### **3.2. Sample Size Considerations**

Approximately 100 subjects who have FGFR3 mutations or fusions based on central genomics laboratory results are planned per each Cohort A-ID and Cohort A-CD. An agent used in the second-line setting that has an ORR of 35% would be considered clinically meaningful. With the assumed rates of 35% for the intervention, a sample size of approximately 100 subjects per each Cohort A-ID and Cohort A-CD would provide a 95% CI with a lower limit of > 25%, assuming 10% lost to follow-up. Approximately 40 subjects will be enrolled in Cohort B (all other FGF/FGFR alterations), which will provide > 80% chance of observing at least 6 responders if the underlying ORR is 20%.

Subjects enrolled without known FGF/FGFR alteration from the sponsor's central laboratory will not be included in the efficacy analyses and may be replaced.

## **4. DATA HANDLING DEFINITIONS AND CONVENTIONS**

### **4.1. Scheduled Study Evaluations and Study Periods**

#### **4.1.1. Day 1**

Day 1 is the date that first dose of study drug (INCB054828) is administered to the subjects.

#### **4.1.2. Study Day**

If a visit/reporting date is on or after Day 1, then the study day at the visit/reporting date will be calculated as

$$\text{Day \#} = (\text{Visit/Reporting Date} - \text{Day 1 date} + 1).$$

If the visit/reporting date is before the Day 1 date, then the study day at the visit/reporting date will be calculated as

$$\text{Day \#} = (\text{Visit/Reporting Date} - \text{Day 1 date}).$$

A study day of -1 indicates 1 day before Day 1.

#### **4.1.3. Baseline Value**

Baseline is defined as the last nonmissing measurement obtained prior to the first administration of INCB054828. When scheduled assessments and unscheduled assessments occur on the same day and time of the assessment or time of first dose is not available, use the following convention to determine baseline:

- If both a scheduled and an unscheduled visit are available on the day of the first dose, and the time is missing, use the scheduled assessment as baseline.
- If all scheduled assessments are missing on the day of the first dose, and an unscheduled assessment is available, use the unscheduled assessment as baseline.

#### **4.1.4. Handling of Missing and Incomplete Data**

In general, values for missing data will not be imputed unless methods for handling missing data are specified in this section or relevant sections.

Partial disease/cancer diagnosis date will be handled as follows:

- If only the day is missing, then the imputed day will be the first of the month.
- If both the month and day are missing, then the imputed day and month will be 01 JAN.
- No imputation will be done if the date is completely missing.

For relevant efficacy endpoints, partial death date will be imputed as follows:

- If mmyyyy for the last contact date = mmyyyy for the death date, then the death date will be set to the day after the last contact date.
- If mmyyyy for the last contact date < mmyyyy for the death date, then the death date will be set to the first day of the death month.
- Otherwise, the partial death date will not be imputed.

#### **4.1.5. Cycle Length and Duration**

Cycle 1 Day 1 is the day that the first dose of INCB054828 is administered. Scheduled cycle length is 21 days, with first day of each cycle corresponding with the first day of INCB054828 administration in that cycle.

#### **4.1.6. Analysis Window**

For parameters that will be summarized by visit, the nominal visit as recorded on the eCRF will be used. There will be no additional analysis windowing done based on the assessment date.

### **4.2. Variable Definitions**

The following variables will only be calculated if not reported on the eCRF.

#### **4.2.1. Age**

Subject age will be calculated as the integer part of the number of years from date of birth to the date of signing the informed consent form, using the following formula:

$$\text{Age} = \text{integer part of } (\text{date of informed consent} - \text{date of birth} + 1) / 365.25$$

#### **4.2.2. Body Mass Index**

BMI will be calculated as follows:

$$\text{BMI (kg/m}^2\text{)} = [\text{weight (kg)}] / [\text{height (m)}]^2$$

#### **4.2.3. Prior and Concomitant Medication**

Prior medication is defined as any nonstudy medication started before the first dose of INCB054828.

Concomitant medication is defined as any nonstudy medication that is started accordingly:

- Before the date of first administration of INCB054828 and is ongoing throughout the study or ends on/after the date of first study drug administration.
- On/after the date of first administration of INCB054828 and is ongoing or ends during the course of study drug administration.

A prior medication could also be classified as "both prior and concomitant medication" if the end date is on or after first dose of INCB054828. In the listing, it will be indicated whether a medication is prior-only, concomitant-only, or both prior and concomitant medication.

For the purposes of analysis, all medications will be considered concomitant medications unless the medications can unequivocally be defined as not concomitant.

## **5. STATISTICAL METHODOLOGY**

### **5.1. General Methodology**

Unless otherwise noted, SAS® software (SAS Institute Inc, Cary, NC; v9.1 or later) will be used for the generation of all tables, graphs, and statistical analyses. Descriptive summaries for continuous variables will include, but not be limited to, the number of observations, mean, standard deviation, median, minimum, and maximum. Descriptive summaries for categorical variables will include the number and percentage of subjects in each category.

### **5.2. Treatment Groups**

This is an open label, single-treatment group study. Subjects will be summarized by cohort and by total.

### **5.3. Analysis Populations**

#### **5.3.1. Efficacy Evaluable Population**

The efficacy evaluable population includes all subjects enrolled in the study who have a known FGF/FGFR alteration from the sponsor's central laboratory and received at least 1 dose of INCB054828. The efficacy evaluable population will be used for analyses of all efficacy data.

#### **5.3.2. Per Protocol Population**

Subjects in the efficacy evaluable population who are considered to be sufficiently compliant with the Protocol compose the PP population.

The following procedures will be performed to identify those subjects who are to be excluded from the PP population before the database freeze:

- Clinical review of Protocol deviations/violations.
- Clinical review of concomitant medications as defined in Section 5.6 of the Protocol.
- Clinical review of the dose administration and drug accountability listing.

The determination of subjects being considered for exclusion from the PP population by the clinical team will be prepared and signed before database freeze.

The PP population will be used in the supportive sensitivity analyses for efficacy endpoints.

### **5.3.3. Safety Population**

The safety population includes all enrolled subjects who received at least 1 dose of INCB054828. All safety analyses will be conducted using the safety population.

## **6. BASELINE, EXPOSURE, AND DISPOSITION VARIABLES AND ANALYSES**

[Appendix A](#) provides a list of data displays and sample data displays.

### **6.1. Baseline and Demographics, Physical Characteristics, and Disease History**

Demographic and baseline characteristics, disease history, and prior therapy will be summarized for the efficacy evaluable population and safety population and listed.

#### **6.1.1. Demographics**

The following demographic characteristics will be summarized for the efficacy evaluable population and safety population (if needed): age, sex, race, ethnicity, weight (by gender), height, and BMI.

#### **6.1.2. Baseline Disease Characteristics**

The following baseline disease characteristics will be summarized for the efficacy evaluable population and safety population (if needed): ECOG performance status and baseline phosphate.

#### **6.1.3. Disease History**

Time since diagnosis, stage at diagnosis, bladder cancer location at diagnosis, histology at diagnosis and baseline, and current TNM classification will be summarized.

Time since diagnosis will be calculated as:

$$\text{Time since diagnosis (years)} = (\text{Day 1 date} - \text{date of diagnosis} + 1) / 365.25$$

#### **6.1.4. Prior Therapy**

Number of subjects who received prior systemic cancer therapy and number of prior systemic cancer therapy regimens, number of subjects who received prior cisplatin, as well as the number of subjects who received prior immune therapy will be summarized for the efficacy evaluable population and safety population (if needed). Immune therapy includes but not is not limited to the following terms: atezolizumab, avelumab, durvalumab, nivolumab, pembrolizumab, tremelimumab, and ipilimumab. Regimen name, component drugs, start and stop dates, purpose of the regimen, best response, reason for discontinuation, and date of relapse/progression will be listed.

Number of subjects who received prior radiation will be summarized for the efficacy evaluable population. Radiotherapy type, body site, start and stop dates, total dose, and best response will be listed.

Number of subjects who had prior surgery or surgical procedure for the malignancies under study will be summarized for the efficacy evaluable population. Date and description of the surgery/procedure will be listed.

### **6.1.5. Medical History**

For subjects in the efficacy evaluable population and safety population, medical history will be summarized by system organ class and preferred term and will be listed.

## **6.2. Disposition of Subjects**

The number and percentage of subjects who were treated, discontinued study treatment with a primary reason for discontinuation, and discontinued from the study with a primary reason for withdrawal will be summarized for the efficacy evaluable population and safety population (if needed).

## **6.3. Protocol Deviations**

Protocol deviations collected on the eCRF will be summarized descriptively and listed.

## **6.4. Exposure**

For subjects in the safety population, exposure to INCB054828 will be summarized descriptively as the following:

- **Number of treatment cycles:** Number of cycles with a nonzero dose of INCB054828
- **Duration of treatment (days):** date of last dose of INCB054828 – date of first dose of INCB054828 + 1
- **Average daily dose (mg/day):** total actual INCB054828 dose taken (mg) / duration of treatment (days)

## **6.5. Study Drug Compliance**

Overall compliance, total prescribed dose, and total actual dose of INCB054828 will be summarized descriptively and listed for subjects in the safety population.

Overall compliance (%) for INCB054828 will be calculated for all subjects as:

$$\text{compliance (\%)} = 100 \times [\text{total dose actually taken}] / [\text{total prescribed dose}]$$

The total prescribed dose is defined as the sum of the doses prescribed by the investigator accounting for dose modifications.

The total actual dose taken will be calculated based on information entered on the drug accountability eCRF. If there is dispensed drug that has not been returned yet, the actual dose

taken starting from the dispense date of the unreturned drug will be imputed by the dose taken as reported on the dosing eCRF.

## **6.6. Prior and Concomitant Medication**

Prior medications and concomitant medications will be coded using the WHO Drug Dictionary. For subjects in the safety population, the number and percentage of subjects with prior and concomitant medications will be summarized by WHO drug class and WHO drug term. In the data listing, each medication will be recorded as prior, concomitant, or both prior and concomitant.

## **7. EFFICACY**

[Appendix A](#) provides a list of data displays and sample data displays.

### **7.1. Efficacy Hypotheses**

Not applicable.

### **7.2. Analysis of the Primary Efficacy Parameter**

#### **7.2.1. Primary Efficacy Analysis**

The primary endpoint of the study is ORR in subjects with FGFR3 mutations or fusions based on the central genomics laboratory results and on a continuous dose regimen, defined as the proportion of subjects with best response of CR or PR based on review of scans by an independent centralized radiological review committee per RECIST v1.1 ([Eisenhauer et al 2009](#)). Confirmation of CR and PR is required and documented in the Independent Review Charter. This analysis will be based on the efficacy evaluable population. Subjects who do not have sufficient baseline or on-study response assessment information to be adequately assessed for response status will be included in the denominators in the calculation of ORR. The 95% CI for the ORR will be calculated using the Clopper-Pearson method.

The ORR will also be analyzed based on the PP population as sensitivity analysis.

##### **7.2.1.1. Response Criteria**

Objective assessment of tumor status will be evaluated by an independent central radiological review committee based on RECIST v1.1, and response status will be logged into the eCRF.

Response status will be recorded at each response assessment visit as CR, PR, SD, PD, or NE.

##### **7.2.1.2. Overall Response Rate and Best Response**

A subject is considered an objective responder if they have a best overall response of CR or PR at any postbaseline visit prior to first PD.

In general, best overall response is the best response recorded postbaseline prior to and including the first PD, in the order of CR, PR, SD, PD, and NE. A best overall response of CR or PR needs to be confirmed, and confirmation method is described in the Independent Review Charter. In the case of SD, measurements must meet the SD criteria at least once after the date of first

dose at a minimum interval of 49 days. Subjects that fail to meet this criterion will have best overall response of PD if the next available assessment indicates PD or NE if there is no additional assessment available.

### **7.2.2. Subgroup Analysis for the Primary Endpoint**

Subpopulation analysis of the primary endpoint will be performed based on appropriate intrinsic and extrinsic factors if needed.

## **7.3. Analysis of the Secondary Efficacy Parameters**

### **7.3.1. Secondary Endpoints Involving Objective Response Rate**

The secondary endpoints involving ORR in this study include the following:

- ORR in subjects with FGFR3 mutations or fusions based on central genomics laboratory results and using an intermittent dose regimen (Cohort A-ID). Response will be based on review of scans by a centralized radiological review committee.
- ORR in subjects with FGFR3 mutations or fusions based on central genomics laboratory results and using a continuous dose regimen (Cohort A-CD) and intermittent dose regimen (Cohort A-ID). Response will be based on review of scans by centralized radiological review committee.
- ORR in all subjects receiving INCB054828 administered as continuous dose regimen and intermittent dose regimen (Cohorts A-ID, A-CD, and B, combined). Response will be based on review of scans by a centralized radiological review committee.
- ORR in subjects with all other FGF/FGFR alterations (Cohort B). Response will be based on review of scans by a centralized radiological review committee.

The secondary endpoints involving ORR will be analyzed in the same way as the primary endpoint, and the 95% CI for ORR will be calculated using exact method for binomial distribution. Confirmation of CR and PR is required and documented in the Independent Review Charter.

### **7.3.2. Progression-Free Survival**

Progression-free survival is defined as the length of time from the start of the study drug (Day 1) to the earlier of death or disease progression by RECIST v1.1, as assessed by the independent centralized radiological review committee. The date of PD will be the timepoint at which progression is first recorded. Censoring for PFS will follow the algorithm outlined in [Table 1](#), which is based on the FDA Guidance for Industry: Clinical Trial Endpoints for the Approval of Cancer Drugs and Biologics ([FDA 2015](#), [FDA 2018](#)).

The number of subjects who progressed or died and the number of subjects censored will be summarized. The Kaplan-Meier estimate of median PFS will be presented with its 95% CI. The 95% CI will be calculated using the Brookmeyer and Crowley's method ([Brookmeyer and Crowley 1982](#)). The PFS analysis will be conducted for Cohorts A-ID, A-CD, and B.

**Table 1: Evaluation and Censoring of Progression-Free Survival**

| Situation  | Outcome | Date of Progression or Censoring  |
|---|----------------|--|
| No baseline tumor assessment                                  | Censored       | Day 1  |
| No adequate postbaseline response assessment                  | Censored       | Day 1  |
| Progression documented between scheduled response assessments | Progressed     | Date of first overall response of progressive disease  |
| No progression  | Censored       | Date of last adequate response assessment (not NE and not missing)   |
| Study discontinuation for undocumented progression            | Censored       | Date of last adequate response assessment (not NE and not missing)   |
| Study discontinuation for toxicity or other reason            | Censored       | Date of last adequate response assessment (not NE and not missing)   |
| New anticancer treatment started                              | Censored       | Date of last adequate response assessment (not NE and not missing) prior to starting of the new anticancer treatment |
| Death before first progressive disease assessment             | Progressed     | Date of death  |
| Death between adequate assessment visits                      | Progressed     | Date of death  |
| Death or progression after more than 1 missed assessment      | Censored       | Date of last adequate response assessment (not NE and not missing)   |

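### SAP Table 1 gives two opposite PFS outcomes for a subject who dies before any adequate postbaseline scan, and does not say which applies

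*SAP*

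**What the plan says.** Protocol 9.4.1.2 and SAP 7.3.2 both define PFS as running from first dose to death or centrally assessed progression, whichever is earlier. For censoring, SAP 7.3.2 says: "Censoring for PFS will follow the algorithm outlined in" Table 1. The relevant rows are:

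- Row 2, "No adequate postbaseline response assessment": censored, Day 1.
- Row 8, "Death before first progressive disease assessment": event, date of death.
- Row 1, "No baseline tumor assessment": censored, Day 1.
- Row 7, "New anticancer treatment started", and the last row, "Death or progression after more than 1 missed assessment": censored at the latest adequate assessment (for row 7, the latest one before the new treatment).

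Neither the table nor the text around it ranks the rows, and the visible Protocol text has no PFS censoring rule of its own. On reporting, SAP 7.3.2 says: "The number of subjects who progressed or died and the number of subjects censored will be summarized". It adds the Kaplan-Meier median with its 95% CI for each cohort, and Figure 4.2.2 in Appendix A is the curve. Protocol Table 4 schedules scans every 9 weeks from the end of Cycle 3, and one at end of treatment.

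**The concern.** Row 2 does not require the subject to be alive, and row 8 does not require an earlier scan. A death before any adequate postbaseline scan therefore fits both, with opposite outcomes and different dates. Row 2 also comes first in what the SAP calls an algorithm, so someone programming the table from the top down would reach it first.

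Censoring such a death at Day 1 contradicts the PFS definition, and it removes the subjects with the worst early outcome from the risk set. The count of subjects who progressed or died would fall by the number of such deaths, and the curve would be too high once those deaths had occurred. The overlap touches PFS by central review and by investigator review (SAP 7.4.2), in Cohorts A-ID, A-CD and B.

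**Working it through.** The plan gives no PFS planning figure, so there is nothing to reproduce. The check has two parts: whether the rows overlap, and what row 2 would do if applied to known deaths.

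**1. Overlap.** Take a subject with a baseline scan who dies at Week 5 with no postbaseline scan. Row 2: there is no adequate postbaseline assessment, so the subject is censored at Day 1. Row 8: death came before any assessment showing progression, so it is an event at Week 5. The last row does not apply, because no scheduled scan has yet been missed. Row 7 does not apply without new treatment. Two rows remain, and they disagree.

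**2. Inputs.** Planned cohort sizes are 100 (A-ID, A-CD) and 40 (B), from SAP 3. The scan interval is 9 weeks, from Protocol 7.6.1 and Table 4. Assumed, because the documents do not give it: d, the fraction dying unscanned, at 2, 5 or 10%.

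**3. Event counts.** Row 2 gives 2, 5 or 10 fewer PFS events of 100, or 1, 2 or 4 fewer of 40.

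**4. Kaplan-Meier values, deaths before Week 9, no other Day 1 censoring.** With n subjects, k = nd unscanned deaths and p progressions at Week 9:

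- Row 8: S(Week 9) = (n − k − p)/n
- Row 2: S(Week 9) = (n − k − p)/(n − k)
- Ratio, row 2 to row 8: n/(n − k) = 1/(1 − d). It carries through to later scans.

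Example with n = 100, k = 5, p = 20: 75/100 = 0.750 against 75/95 = 0.789.

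| n | k | ratio |
|---|---|---|
| 100 | 2 | 1/0.98 = 1.020 |
| 100 | 5 | 1/0.95 = 1.053 |
| 100 | 10 | 1/0.90 = 1.111 |
| 40 | 1 | 1/0.975 = 1.026 |
| 40 | 2 | 1/0.95 = 1.053 |
| 40 | 4 | 1/0.90 = 1.111 |

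If a fraction c is also validly censored at Day 1 (alive, never scanned), the ratio is (1 − c)/(1 − c − d). With c = 5% it is 95/93 = 1.022, 95/90 = 1.056 and 95/85 = 1.118.

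**5. Deaths after one missed scan.** Put the 5 deaths at Week 12 instead, with the Week 9 scan missed and 20 progressions at Week 9. At Week 9, row 8 gives 80/100 = 0.800 and row 2 gives 75/95 = 0.789, slightly the other way. From Week 12 the values are 75/100 = 0.750 and 75/95 = 0.789, a ratio of 1.053 again. So the ratio in step 4 holds only after the last such death.

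**6. Median (deaths before Week 9).** The row 2 value is the row 8 value divided by (1 − d). The median moves to a later scan only if the row 8 value at the median scan lies between 0.50(1 − d) and 0.50. The lower bound is 0.490, 0.475 or 0.450 for d = 2, 5 or 10%. Twenty-four expected-value scenarios were run: exponential PFS with an assumed median of 3, 4, 5 or 6 months, applied to scanned subjects only or to all subjects, 9-weekly scans, and the three values of d. The median stayed on the same scan in 20. The other 4 moved one scan later, all with a 4- or 6-month median applied to all subjects and d = 5 or 10%. For example, 4 months is about 17.39 weeks, so the Week 18 value is 0.5^(18/17.39) = 0.488. That is above 0.475 and 0.450 but below 0.490.

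**The case against.** The strongest reply is that the documents already point to one answer. Both PFS definitions count death. SAP 10.1 declares no changes to Protocol-defined analyses. Row 8 names death and row 2 does not, and if row 2 prevailed, row 8 would lose its most obvious subjects. All of this stands, and it is why the event is the better reading. It does not amount to a stated rule. Nor can a programmer fall back on death always being an event, because the last row deliberately censors some deaths.

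Other parts of the reply also stand:

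- Row 1 is nearly empty for deaths, since measurable disease and a screening scan are required.
- Row 4, "No progression", naturally excludes deaths, because the table labels deaths in rows 8 and 9 as progressed. It needs no change.
- d is not documented. The end-of-treatment scan and the 12-week life-expectancy criterion (Protocol 3.1) should keep it small.

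A reader might infer more: that the plan drops early deaths from PFS, or that median PFS will be visibly inflated. The documents support neither. Nothing shows that row 2 would be applied to known deaths. If event times are treated as continuous, with an assumed 4- or 6-month median, the median differs by about 0.1 to 0.9 months for 2 to 10 deaths in 100. That ignores the 9-weekly scans, on which most progression dates will fall.

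**Conclusion.** The conflict is real: two stated rules give opposite outcomes for the same subject, and no precedence is given. It is more than a missing detail, because row 2 read literally contradicts the PFS definition. Under row 8 there is no effect. Under row 2 the size is as computed above: 2 to 10 fewer events per 100, and Kaplan-Meier values from Week 9 higher by a factor of 1.02 to 1.11. This rests on an assumed d of 2 to 10%, deaths before the first scan and no other Day 1 censoring. The median would usually not move.

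The scope is secondary PFS, in a plan whose analyses are all declared exploratory (SAP 3.1). The primary ORR is untouched, because subjects who cannot be assessed stay in its denominator (SAP 7.2.1). DOR uses the same censoring table but is also untouched, since every responder has an adequate postbaseline scan. The wording should be corrected, but the conflict does not threaten the trial's main result.

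**What to change.** 1. Add *and no death* to row 2, and to row 1 for consistency. A death before any adequate postbaseline scan is then an event on its date under row 8, unless row 7 or the last row already censors it.
2. In row 7 and the last row, state that the censoring date is Day 1 when there is no adequate postbaseline assessment. Row 2 supplies that date now and would no longer do so for subjects who die.

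For a never-scanned subject, the retained exceptions are a death after new anticancer treatment, and a death after both the Week 9 and Week 18 scans were missed. These are choices Table 1 already makes, and the edit leaves them alone. The rest of the table needs no re-ranking. A blanket order that put the missed-assessment row first could wrongly censor a subject who missed two scans, resumed scanning and then progressed.

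The cost is a few words in four rows of the SAP and no new data. PFS may look slightly less favourable than under a literal row 2.
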